## 5. 4 STUDY DESIGN

### 1. 4.1 OVERALL DESIGN

This study is a partially nested randomized controlled trial research design (PN-RCT) with a two-level structure of clients (level-1) nested within callers (level-2) for the two treatment conditions

which receive calls. Given that outcomes for older adults receiving calls from the same volunteer may be more similar than for those who receive calls from a different volunteer, the use of multilevel modeling can account for these data dependencies.

We will be investigating 1) how our *BE WITH* innovation reduces social isolation, loneliness, and elevated suicidality among HDM and former CM clients and improves their social support and well-being. Social isolation, loneliness, and elevated suicidality will be operationalized through a combination of validated psychometric measures taken before, during, and after the structured 8-week intervention. For older adults receiving calls, data from validated measures will be triangulated with behavioral observations of the older adults' emotional states based upon a structured analysis of recorded audio files.

We hypothesize that older adults in both treatment conditions will have *reduced: social isolation, loneliness, depression, anxiety, mental health distress, and suicide desire*; and they will have *increased: social connection, social support, and well-being* over time and in comparison to those in the control condition.

We will also investigate 2) how *BE WITH* improves the frequency of empathic and suicide intervention best practice behaviors by NS volunteers to older adult participants that have heightened social isolation, loneliness, and elevated suicidality. This will be demonstrated in both real-world settings and in situations where a *research confederate* presents a clinically heightened risk of social isolation, loneliness, and elevated suicidality. Evaluation of counseling or suicide intervention skills is challenging, as observations of caregivers working with clients are required.

We hypothesize that those trained in both conditions will demonstrate *positive global counseling behaviors*; however, those trained in *BE WITH* will more often employ *suicide intervention practices* when needed.

Measured Outcome	Sample	Data Collection / Tracking

Reduction in loneliness, elevated suicidality, and improved social support/well-being for older adult clients
 
Validated constructs (see appendix D):
 
Loneliness (UCLA); Social Support (SPS); Suicide -- Risk (SBQ-R); Suicide Desire (INQ); Suicide Capability (FAD); Depression (PHQ); Anxiety (GAD); Distress (K6);
	
540 Clients, randomly assigned to 3 conditions. This includes the 2 tx conditions and a control that receive no calls
 
Stratified random sampling by 3 levels of loneliness and suicidality (low, medium, and high risk tiers)
	
Data collection for older adult participants:
 
 
· pre intervention (baseline)
 
· measurement occasions every 2 weeks (total of 5 measurement occasions)
 

Improved frequency of empathic and suicide intervention best practice behaviors by NS volunteers
 
Coded constructs: Adapted observation protocol.
	
60 Volunteers, randomly assigned to 2 conditions.
 
 
· BE training only
 
· BE WITH (BE training plus ASIST)
 
 
Those trained in BE will be offered ASIST after the study.
	
Preceding the intervention study, all volunteers receive BE (phone-based social connection) training. BE WITH volunteers will be given the standardized and manualized ASIST training (if they have previously received ASIST, they will be provided with the ASIST refresher training).

---	---	---

**Validated outcome measures** are essential for effective evaluation of any mental health or suicide prevention programming. While the social isolation, loneliness, and elevated suicidality constructs we will study are listed in the following table, the specific psychological scales that measure them are listed and explained in Appendix D. The comprehensive battery of assessments has been field tested and well received by older adults (Appendix D). We have also completed cognitive interviews (administered questions and sought feedback on the experience from older adults), and trained data collectors to use a conversational style in speaking with participants. Short forms of several of these measures will be completed weekly by the older adults and take 15 minutes to complete.

Analyses will investigate the effect of treatment conditions (BE, BE WITH, and control) on post-intervention outcomes (i.e. endpoints) while controlling for baseline responses (prior to intervention). Furthermore, analyses will explore differences between treatment conditions in longitudinal trends of client state as well as how volunteers utilize specific intervention skills over time. For this longitudinal data, a lower level of nesting will be included in the analysis: weekly call and state data (level 1) nested within older adults (level 2) nested within volunteers (level 3). However, the PN-RCT design would only have levels 1 and 2 for the control group.

## 2.

## 4.2 SCIENTIFIC RATIONALE FOR STUDY DESIGN

Due to increased social isolation and loneliness in older adults, experts have called for innovative approaches to address them, including “training nontraditional groups to provide psychological first aid, helping teach the lay public to check in with one another and provide support.” The aging services network (ASN) has made concerted efforts to reconfigure key programs to protect older adults and is prioritizing programs that can be delivered remotely. AAdvancing States has described how community-based organizations are launching programs intended to address social isolation and loneliness, with **phone-based social connection** identified as a promising strategy to engage volunteers and support at-risk older adults. In April 2020, the National Council On Aging (NCOA) surveyed community-based organizations about older adult clients’ needs, and 62% described “staying socially connected while physically distancing” as a “high priority.” Meanwhile, the report indicated due to the pandemic, the need for home-delivered meals (HDMs) increased while that for other programs (e.g., chronic disease self-management, falls prevention, caregiver support) decreased.

In May 2020, we developed guidelines for the Administration for Community Living (ACL) regarding how nutrition services (NS) volunteers can foster and maintain meaningful connections with socially isolated older adults. That document, *Enhancing Socialization through Making Meaningful Volunteer Connections* (Appendix B), provides 15 recommendations for engagement in phone-based social connection. Although these programs are in early stages of

development within the ASN, there is evidentiary support that key skills such as active listening, empathy, and promoting a sense of belonging may be vitally important. Unfortunately, no programs on the NCOA Evidence-Based Registry address social isolation, loneliness, and elevated suicidality. Our innovation seeks to remedy that.

### 3. 4.3 JUSTIFICATION FOR INTERVENTION

Many older adults who are at-risk for social isolation, loneliness, and elevated suicidality are also at risk for food insecurity or institutionalization. The Older Americans Act (OAA) Nutrition Program that includes congregate meal (CM) and HDM is *the largest and primary program* within home and community-based services (HCBS), making it a strategic context to address other issues, such as social isolation, loneliness, and elevated suicidality, among at-risk older adults. Many homebound older adults have limited social contacts, including 20% who have infrequent contact with friends or family. NS volunteers often form an important part of older adults' social support networks. In previous research, measures of loneliness and well-being improved for older adults after just two months of receiving HDM services. Consistent with a public health approach to prevention, NS volunteers already function as ***natural helpers***, defined by suicide researchers as those "who already have close communication" with older adults either through their "ongoing job role" or by "virtue of personal qualities, such as warmth and empathy." Volunteers from NS programs may be among very few individual(s) who interact on a *regular basis* with older adults receiving NS. This is particularly relevant to supporting older adults' mental health because depression rates are three times higher in older adults who require in-home care compared to community samples, and 13.4% of HDM clients reported suicidal thoughts to a volunteer. NS volunteers are vital in helping these older adults remain safe and in the community.

*Our team* has previously established the ASN is a strategic context to address suicide risk, and NS volunteers are uniquely positioned to intervene due to their regular and ongoing interactions with older adults, due to their pre-established relationship with them. Our previous work equipping NS volunteers with evidence-based skills to intervene with older adults experiencing suicidality is, to our knowledge, the first of its kind (ACL grant 90INNU0010-01-00). In our analysis we found NS volunteers were able to learn suicide intervention skills effectively (significant pre to posttest changes, high effect size) and utilize them to provide social support. Furthermore, they exhibited increased comfort, competence, and confidence about responding to older adults at risk of suicide. County leadership reported trained volunteers were "more aware", "more likely to pick up extra shifts", and "more invested" (see Cobb letter of support). NS volunteers demonstrated increased awareness of older adult mental health needs, and were better equipped to respond to suicide risk. Although this training was only in one system for a limited time, more than 30 interventions were tracked, including some over the phone. These findings provide a proof of concept for having NS volunteers address social isolation, loneliness, and elevated suicidality alongside their role in delivering meals, and that additional investigation of such trainings could well demonstrate the outcomes with older adults required for eligibility on the NCOA registry.

### 4. 4.4 END-OF-STUDY DEFINITION

A participant is considered to have completed the study if he or she has completed the baseline assessment, 4 additional measurement occasions evaluating the treatment (8 weeks of treatment call dosages).

## 6. 5 STUDY POPULATION

### 1. 5.1 INCLUSION CRITERIA

In order to be eligible to be a **participant** in this study, an individual must meet all of the following criteria:

1. Provision of verbal informed consent
2. Classify as an Older Adult (65+)
3. Stated willingness and ability to comply with all study procedures
4. Receive nutrition services through the Aging Services Network (i.e. either HDM (home delivered meals services) or CM (congregate meals))
5. Be affiliated with one of the 25 senior centers we will contract with through a Memorandum of Understanding

In order to be eligible to be a **trained helper** in this study, an individual must meet all of the following criteria:

1. Provision of written informed consent
2. State willingness to comply with all study procedures
3. Be a staff or volunteer within the ASN (Aging Services Network), specifically within the 25 senior centers we are working with
4. Meet criteria for being a “natural helpers” (i.e. be warm, empathic, and having ongoing interaction with participants through one’s job role)
5. Be recommended by the senior center leadership as meeting these qualifications

### 2. 5.2 EXCLUSION CRITERIA

**Exclusion criteria for Participants:** An individual who meets any of the following criteria will be excluded from participation in this study:

1. Had a dementia diagnosis, or another form of cognitive impairment, and/or hearing impairment that would preclude phone conversation.
2. Participation in another warm calling behavioral treatment or intervention study simultaneously occurring in this state

The reasons given to exclude participants with dementia/cognitive impairment diagnoses from large-scale clinical research are partially related to the concern of a potential risk of abuse and exploitation. Further, those with cognitive impairment are not able to give informed consent, and there are measurement challenges with behavioral health data.

**Exclusion criteria for trained natural helpers:** An individual who meets any of the following criteria will be excluded from participation in this study:

1. Does not have ongoing interactions with potential old adult participants (i.e. is a part of an optimized nutrition service provider in which they do not serve the same older adults consistently over time)
2. Participation in another warm calling behavioral treatment or intervention study simultaneously occurring in this state

### 3. 5.3 LIFESTYLE CONSIDERATIONS

N/A

### 4. 5.4 SCREEN FAILURES

Screen failures are defined as participants who consent to participate in this study but are not subsequently randomized and assigned to one of the 3 treatment conditions. Individuals who do not meet the criteria for participation in this trial (screen failure) because of meeting one or more exclusion criteria (i.e. cognitive impairment) will be removed from the study.

If participants drop out between being consented, randomized, and assigned, they will have the opportunity to be rescreened and join a subsequent wave of treatment.

### 5. 5.5 STRATEGIES FOR RECRUITMENT AND RETENTION

To adequately power the PN-RCT we need 540 participants. We plan to recruit and screen three times that number, and enroll a minimum of 200 more, to account for potential attrition issues.

Recruitment strategies include the following:

1. Flyers to be provided to older adults receiving HDM through their home delivered meal provider along with their meal
2. Announcements of the study opportunity to be received by older adults through their case managers
3. After 1 and 2, graduate research students will make personalized calls to the older adults to go over the recruitment script and study procedures.

Sample information to be provided to older adults:

*You are invited to take part in a research study. It is up to you to decide if you would like to take part in the study. The purpose of the study is to investigate the BE WITH innovation. You are invited to participate because you are a recipient of HDM services in X county. A total of 540 older adult clients receiving HDM will be included in the study. If you choose to participate, you will take a survey that will determine your eligibility, and you will be compensated for your time to take this survey. Your role in the study will take place over an 8-week period. Depending on your randomly assigned group, this time may be spent talking on the phone, and/or answering a short survey. The risks of being in this study include potentially having more worry or anxiety. This study is designed to benefit you, as the BE WITH program is designed to give more interpersonal connections to older persons. Overall, we hope to gain information about how nutrition services can provide more support to older adult clients.*

*The purpose of the study is to investigate the BE WITH training for nutrition service volunteers and understand how it impacts the wellbeing of nutrition service clients. You are invited to take part in this research study because you are, or have recently been, a nutrition service client. A total of 60 volunteers will be invited to take part in this study along with up to 540 older adults.*

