## 2.

### 2.3.2 KNOWN POTENTIAL BENEFITS

**Immediate potential benefits:** Social support has been proven across hundreds of behavioral health studies to be one of the strongest predictors of positive psychological outcomes following disaster. Research has also shown that connecting with others during crisis, disaster (i.e. pandemic) is helpful in the immediate. Across disasters talking about, expressing, and feeling one's feelings has been found to set persons apart from those that do not in terms of faring better as a result of experiencing crisis/disaster.

**Long term potential benefits:** Overall, we hope to gain information about the BE WITH innovation, and ideally submit BEWITH to be accepted on the National Council on Aging's (NCOA) evidence-based registry to enable warm calling programs to occur across the US. Currently, there is no program to make warm calls, or visits remotely on the NCOA registry, so the older adult participants in this study will be made aware (in the informed consent) of this larger purpose and that they are helping contribute to bringing these types of warm calling programs to older adults across the country.

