## 7. 6 STUDY INTERVENTION(S) OR EXPERIMENTAL MANIPULATION(S)

### 1. 6.1 STUDY INTERVENTION(S) OR EXPERIMENTAL MANIPULATION(S) ADMINISTRATION

#### 1. 6.1.1 STUDY INTERVENTION OR EXPERIMENTAL MANIPULATION DESCRIPTION

The BE WITH program is grounded in (1) the Befriending and Narrative Reminiscence literature which are best practices in working with older adults, and (2) the Interpersonal Psychological Theory of Suicide (ITPS). BE WITH includes an 8-week warm calling treatment that is delivered to older adults (racially and economically diverse, urban, suburban, and/or rural). At the start of the program, older adults are asked to reminisce about their life, and provide the treatment provider some information that can be built upon in subsequent call dosages (see graphic below).

Each week an older adult participant will receive a 20-30 minute "call dosage" from treatment providers that are trained in 1 of 2 protocols:

**(a) BE condition** which involves receiving call dosages from providers trained to foster **belongingness** and **empathy** (2 hours), grounded in the befriending literature, and narrative reminiscence. Aging Network Providers trained in BE provide a "small dose of sincere connection", through **narrative reminiscence**, and the "**befriending**" strategies.

While the majority of the warm calling of BE WITH centers on this basic connections intervention, there will also be individuals who need more than connection, but rather targeted intervention as approximately 20% of older adults receiving home and community-based services are at risk of suicide.

**(b) BE WITH condition** includes receiving call dosages from providers trained in BE + the aging variant of LivingWorks ASIST (Applied Suicide Intervention Skills Training). Those older adults assigned to this treatment condition will have both the connections intervention, as well as suicide interventions in the chance that one is needed.

**(c) control group** includes no treatment, or call dosages. Every two weeks graduate research students administer the measureset, just as they did for the 2 treatment conditions.

The same time intervals of outcome measures are administered across all 3 conditions.

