## 3. 6.4 STUDY INTERVENTION/EXPERIMENTAL MANIPULATION ADHERENCE

Participants' adherence to the study procedures will be tracked in two ways: (1) through the Friendlybuzz system (tracking adherence to the treatment), and (2) through lab tracking documents (adherence to the measurement, data collection). The Friendlybuzz system will allow us to track in real time the call dosages as they are coming in, the duration of those, timing, etc. The lab tracking documents will enable us to know which participants need the next measurement occasion for data collection. These two

processes remain separate and distinct, to ensure that the treatment is distinct from the measurement of the treatment.

Treatment providers are required to complete training a priori, and utilize the documents and tools (i.e. guidelines for making sincere connections, reminiscence table whereby there are questions provided in each area of the older adults life for the treatment provider to track and follow up on in subsequent sessions, etc.) provided to them to deliver 8 high quality treatment dosages to their caseload of older adult participants that are 20-30 minutes in duration each. They are required to track that, as well as attend weekly supervision and check in with a supervisor who is tracking their treatment delivery through the Friendlybuzz system.

Participants are required to complete a “participation plan” which will be mailed to them after they are baselined, meet eligibility criteria and are randomized. Those randomized to one of the two treatment conditions are required to participate in 8 call dosages and 4 additional measurement occasions. Those randomized to the control group are required to participate in 4 additional measurement occasions and provided with the option to receive 8 call dosages 2 months later (delayed waitlist control).

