### 2. 9.2 SAMPLE SIZE DETERMINATION

To determine appropriate sample sizes, we used formulas developed for PN-RCTs with continuous outcomes and binary outcomes as well as results from a closely related study that tested the effect of the ASIST intervention with similar outcome measures. To detect an effect size of .40 with a continuous outcome, utilizing a Type I error rate of .05, power of .80, ICC of .20, and R^2 of .50 (for baseline covariate), we need 270 older adults with 30 volunteers each calling 6 older adults. For a binary outcome under the same assumptions, we would require 414-522 older adults with 46-58 volunteers for most estimates of the probability of an outcome in the treatment and control groups. Recruiting 540 older

adults (180 in each condition) and 60 volunteers (30 for each treatment condition) provides an adequate sample to evaluate major effects of interest in all proposed analyses.

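### The sample recruitment script tells every candidate the study is designed to benefit them, which may add to the expectancy bias already present in an unmasked comparison of calls with no calls on self-reported scales

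*Combined protocol and SAP*

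**What the plan says.** Section 5.5 gives sample information for older adults, used when candidates are called about the study. It includes the sentence "This study is designed to benefit you, as the BE WITH program is designed to give more interpersonal connections to older persons", with no qualifier for people who will not be called. The same text says "Depending on your randomly assigned group, this time may be spent talking on the phone, and/or answering a short survey" and "The risks of being in this study include potentially having more worry or anxiety".

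Section 2.3.2 says participants will be told, in the informed consent, that "they are helping contribute to bringing these types of warm calling programs to older adults across the country".

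Section 6.1.1 says the control group "includes no treatment, or call dosages". Section 9.2 allots 180 older adults to each of three conditions. Under Section 6.4, controls are "provided with the option to receive 8 call dosages 2 months later (delayed waitlist control").

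Participants are told their condition at a call-back before treatment begins (Sections 1.3 and 10.1.1.2). All assessments are read out by phone and answered by the participant (Section 8.1). Section 6.3 separates the data team from the treatment team, but describes no masking of participants and does not say that data collectors are unaware of the arm.

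**The concern.** Before randomization, a candidate hears that the study is meant to do them good through a named program. They then learn whether they will be called, and for 8 weeks they rate their own loneliness, mood and support aloud to a member of the research team. Called participants may report more improvement because they expect it. Uncalled participants may report less because they are disappointed. Both shifts widen the contrast with control, which is the primary hypothesis in Section 9.1.

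No planned analysis can separate such a shift from a treatment effect. Adjustment for baseline (Section 9.4.2) does not help, because baseline is answered before allocation is known and the shift would arise afterwards. The plan also has no attention control.

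**Working it through.** **Share without calls.** 180/540 = 1/3 receive no calls during the 8 weeks. The other two thirds receive calls of one kind or the other.

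**Which outcomes are exposed.**
- The participant scales in the Section 8.1 table (UCLA, SPS-5, GAD-7, PHQ-9, SF-12 and the INQ subscale) are all answered by the participant.
- Some planned outcomes are not self-report: behavioural observation of older adults from recordings (Section 4.1), independent double coding of helpers (Section 3) and the SIRI-2 (Section 9.4.3).
- None of these can check the contrast with control. Controls have no calls to record, and the SIRI-2 is measured on helpers.

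**The plan's sample size, as a check on the formula.** Section 9.2 gives effect 0.40 SD, Type I error .05 (two-sided assumed), power .80, ICC .20, R² .50 and 6 clients per volunteer. For one calling arm against control:

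SE² = (1 − R²) × [(1 + (6 − 1) × ICC)/n_called + 1/n_control]

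The clustering factor is 1 + 5 × .20 = 2. With 15 volunteers per calling arm, n = 15 × 6 = 90 per arm. Then SE² = .5 × (2/90 + 1/90) = .0167, SE = .129 and 0.40/.129 = 3.10. A noncentral t with 14 df gives power .821. Total 3 × 90 = 270 with 30 volunteers, which matches the stated figure.

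**Planned size, 180 per arm.** SE = √[.5 × (2/180 + 1/180)] = .0913 SD. By normal approximation, significance is reached at 1.96 × .0913 = 0.18 SD at .05, or 2.576 × .0913 = 0.24 SD at .01, the level in Section 9.4.1.

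**Illustration.** The documents give no size for a reporting shift, so the first column is assumed. With no true effect, the chance of a significant result on one outcome (two-sided) is:

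| Net shift, called minus control (SD) | at .05 | at .01 |
|---|---|---|
| 0.05 | 8.5% | 2.2% |
| 0.10 | 20% | 7.0% |
| 0.20 | 59% | 35% |
| 0.30 | 91% | 76% |

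The shift here is the total from all causes. The table does not say how much of it the script would produce.

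**The case against.** The strongest reply is that all arms hear the script alike, before randomization. Any difference between arms comes from later knowing whether one is called, and a design that compares calls with no calls cannot hide that. This stands. The wording can add to the bias but is not its main source, and better wording will not remove it.

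A reader might infer more than the documents support:

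- *That benefit is promised.* The sentence speaks of what the study is designed to do. The sentence before it states a risk, and the script already discloses random assignment and a possible survey-only role. It does not say that benefit is unknown, or plainly that some people get no calls for 8 weeks.
- *That the sentence fits only the one third in the BE WITH arm.* Section 6.1.1 also uses the program's name for the calling treatment as a whole, under both training protocols. Two thirds receive calls during the trial.
- *That controls get nothing.* They may take calls 2 months later, so the gap concerns the 8-week comparison only.
- *That every outcome in the trial is self-report.* Only the participant scales compared with control are all of that kind.
- *That consent lacks neutral wording.* The Section 5.5 text is a sample, the consent pages were not available, and Section 1.3 lists a consent for each condition. Section 2.3.2 shows only what is intended.

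**Conclusion.** The point holds as a minor, inexpensive improvement. A benefit statement with no qualifier for the uncalled third, together with a planned consent message about spreading the program, may increase expectancy and disappointment in a comparison that is unmasked and self-reported. The size cannot be estimated from the documents.

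The thresholds of about 0.18 SD (.05) and 0.24 SD (.01) rest on the Section 9.2 inputs, two-sided tests and a normal approximation. They show that a modest total shift could matter. They do not show that this sentence causes one. An assumed 0.20 SD shift, for example, would pass the .05 threshold by itself but not the .01 threshold.

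**What to change.** 1. In the recruitment script, replace the benefit sentence with neutral text, for example: *We do not know whether these calls help. By chance you may receive one of two kinds of weekly calls, or surveys only during the 8 weeks with the option of calls later.*
2. Keep the registry purpose in the consent, stated neutrally as a reason for the research. Deferring it to a debrief would withhold a purpose that Section 2.3.2 deliberately discloses, and is not advised. Neutral arm labels would achieve little, since they cannot hide whether a person is called.
3. Name expectancy in the plan and the report as a limitation of every comparison with control on self-reported scales.

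Cost: an IRB amendment, which the Statement of Compliance already requires for changes of this kind, and possibly a small drop in recruitment. If enrolment has begun, use the new text for the remaining cohorts and record which text each cohort heard.
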